## 1 PROTOCOL SUMMARY

### 1.1 SYNOPSIS

Title:	The interaction between diabetes and estradiol on human brain metabolism in postmenopausal women
Study Description:	Epidemiological studies suggest there may be an interaction between type 2 diabetes and estrogen in postmenopausal women, such that diabetes may interact with estrogen levels over time to increase risk for dementia. The mechanism for this effect is now known. However, animal research suggests that it may occur through estrogen's effects on cellular metabolism of glucose and ketone bodies. The primary aim of this study is to test whether type 2 diabetes interacts with estradiol on brain metabolism in vivo in humans. This will be accomplished by imaging brain metabolism using positron emission tomography before and after short-term administration of transdermal 17 $\beta$ -estradiol in 10 postmenopausal women with diabetes and 10 non-diabetic postmenopausal women.
Objectives:	
Primary Objective: The primary objective is to determine whether the effects of glucose and ketone body uptake to the brain in response to 8-week administration of transdermal 17<math>\beta</math>-estradiol differ in postmenopausal women with and without type 2 diabetes.
 
Secondary Objectives: Secondary objective: 1) Determine whether 8-week administration of transdermal 17<math>\beta</math>-estradiol alters cognitive performance in postmenopausal women with and without type 2 diabetes.

Endpoints:	
Primary Endpoint: Glucose and ketone body uptake in brain measures with positron emission tomography. Regions of interest include the posterior cingulate, temporal cortex, and prefrontal cortex.
 
Secondary Endpoints: Cognitive function assessed using composite scores of short-term memory and executive functioning. The short-term memory composite will be generated by summing z-scores from Story Recall, List Learning, and computerized tasks. The executive function composite will be generated by summing z-scores of Trails part B-A, computerized tasks, and semantic access (letter and category word fluency).

Study Population:	Postmenopausal women aged 60-80 years old will be recruited, 10 with type 2 diabetes and 10 without from the region of Forsyth County, North Carolina.
Phase:	N/A

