## 3 OBJECTIVES AND ENDPOINTS

OBJECTIVES	ENDPOINTS	JUSTIFICATION FOR ENDPOINTS
Primary:		

OBJECTIVES	ENDPOINTS	JUSTIFICATION FOR ENDPOINTS
To assess whether 8-week administration of estrogen alters brain glucose and ketone body uptake in women with and without type 2 diabetes.	Brain uptake of glucose and ketone bodies using [F-18]FDG PET and [C-11]AcAc PET.	Using PET tracers allows direct measurement of ketone and glucose uptake to the brain.
Secondary		
To assess whether 8-week administration of estrogen alters cognitive test scores in women with and without type 2 diabetes.	Composite scores of memory and executive function.	The cognitive tests selected are commonly used to assess for dementia and dementia risk.

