## 4 STUDY DESIGN

### 4.1 OVERALL DESIGN

This is an investigation of the effects of transdermal estrogen administration on brain uptake of glucose and ketone bodies in postmenopausal women with and without T2D. The main hypothesis is that estrogen affects brain metabolism of ketone bodies and glucose differently in women with T2D and those without, in accordance with the healthy cell bias theory of estrogen action. All women will be tested before and after 8-week estrogen administration. It is a single-site study with two comparison groups: one with T2D (n=10) and one without (n=10). Randomization is not possible, as the comparison is between women affected and unaffected by T2D (and women cannot be randomized to have T2D). The study will include women of European American and African American descent and with Hispanic ethnicity in proportion to the local population for this age group. No interim analysis is planned.

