## 9 STATISTICAL CONSIDERATIONS

### 9.1 STATISTICAL HYPOTHESES

**Aim 1. Assess whether T2D alters cognitive response to 8 weeks of transdermal estrogen.** Composite z-scores will be calculated by calculating a z-score for each cognitive task and summing z-scores for the tasks designated as Short-Term Memory (STM Composite) and Executive Function (EF Composite). We will assess differences in follow-up scores between intervention groups using ANCOVA after covariate adjustment for baseline scores using SAS software. Because age, BMI, and education may influence changes in cognition over time (e.g. learning effects), we will assess whether including these as

covariates affects results. The primary outcomes will be the composite scores. Secondary analyses will examine individual components.

**Aim 2. Assess whether T2D alters estrogen effects on brain uptake of glucose and ketone bodies in whole brain and Alzheimer's disease (AD) related regions of interest.** FDG and AcAc PET scan data will be analyzed with PMOD® Software using methods described by our collaborators. Briefly, imaging data are co-registered to T1 structural MRI data to conduct region of interest (ROI)-based analyses. This will quantify absolute global and regional uptake of FDG and AcAc to determine uptake, as well as uptake of AcAc relative to FDG to find potential areas of compensatory ketone use. T1 MRI images will be processed using publically available software in a customized workflow, primarily ANTs due to evidence of superior performance. Average values for ROI will be calculated for the posterior cingulate/precuneus, temporal lobe, and prefrontal cortices, as these are regions of observed decreases in FDG uptake in AD and are relevant for development and progression of dementia. Inference will be based the same approaches as for cognitive data for 1) whole-brain glucose uptake, 2) whole-brain ketone uptake, 3) regional glucose uptake, 3) regional ketone uptake, 4) whole-brain ratio of ketone/glucose uptake, and 5) regional ratio of ketone/glucose uptake. We will assess inter-relationships among changes in these outcomes and with changes in cognitive function using principal components and canonical correlation.

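### PET uptake is the primary endpoint, but Section 9 ranks none of its PET tests and applies p<0.05 to all analyses with no multiplicity rule

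*Combined protocol and SAP*

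**What the plan says.** The Synopsis (1.1) is explicit about the order of the questions: "The primary aim of this study is to test whether type 2 diabetes interacts with estradiol on brain metabolism". Its primary endpoint is "Glucose and ketone body uptake in brain measures with positron emission tomography", followed by "Regions of interest include the posterior cingulate, temporal cortex, and prefrontal cortex". Its secondary endpoint is "Cognitive function assessed using composite scores of short-term memory and executive functioning". Section 3 keeps that order, and Section 4.1 says: "The main hypothesis is that estrogen affects brain metabolism of ketone bodies and glucose differently in women with T2D and those without".

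Section 9.1 reverses the order of presentation. Cognition is Aim 1, analysed by ANCOVA of follow-up on group with baseline as covariate, and that paragraph contains the sentence "The primary outcomes will be the composite scores". The sentence after it assigns the individual components to secondary analyses. PET is Aim 2 and uses the same approach for six items (two of them carry the number 3): glucose uptake, ketone uptake and the ketone/glucose ratio, each for whole brain and by region. Three regions are defined, one of them as posterior cingulate with precuneus, whereas 1.1 names the posterior cingulate only. No item is called primary.

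Section 9.4.1 sets the significance level at 0.05 for all analyses. The documents contain no testing order, multiplicity adjustment or rule for success on the primary objective.

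**The concern.** A reader who wants to know whether the primary objective was met cannot tell from Section 9 which p-value answers it. It could be whole brain or a region, glucose or ketones, absolute uptake or the ratio. Each is tested at 0.05 and none outranks the others.

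The plan therefore allows the measure that answers the primary question to be picked once the results are known. The stated 5% would then not be the probability of wrongly declaring that diabetes modifies the effect of estradiol on brain metabolism.

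**Working it through.** **Figures in the plan.** There is nothing to reproduce. Section 9.2 gives no effect size, standard deviation or power, and no correlations between measures appear. The usable inputs are 10 women per group (1.1, 4.1), two tracers and three regions (1.1, 9.1), baseline-adjusted ANCOVA (9.1) and 0.05 per analysis (9.4.1). Two-sided tests are assumed, since sidedness is not stated.

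**Number of PET tests, at one value per region.**
- Whole brain: glucose, ketone, ratio = 3.
- Regional: 3 measures × 3 regions = 9.
- Total: 3 + 9 = 12. The six regional uptake tests (2 tracers × 3 regions) match the measures that 1.1 names.

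**If the tests were independent.** P(at least one false positive) = 1 − 0.95^k.
- k = 6: 1 − 0.95^6 = 26.5%.
- k = 12: 1 − 0.95^12 = 46.0%.

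**With correlation.** Uptake measures from the same scan will be correlated, which lowers these figures. All correlations below are assumptions. Each result is a simulation of 20,000 null trials with 10 women per group and no baseline difference between groups.

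| Tests | Assumed correlation | Chance of at least one false positive |
|---|---|---|
| 6 regional uptake tests (ANCOVA) | within tracer 0.5 | about 24% |
| 6 regional uptake tests (ANCOVA) | within tracer 0.9 | about 16% |
| 6 regional uptake tests (ANCOVA) | within tracer 0.95 | about 14% |
| all 12 (two-sample t tests) | common 0.3 | 41% |
| all 12 (two-sample t tests) | common 0.5 | 33% |
| all 12 (two-sample t tests) | common 0.8 | 19% |

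The ANCOVA rows take a between-tracer correlation of 0.3 and baseline/follow-up correlations of 0.5 and 0.8. Varying the between-tracer value from 0 to 0.6 moves them by a point or two. A single common correlation is a simplification for the 12 tests, because the ratios are built from the other measures.

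**With two primary tests under Holm.** A false positive under the joint null needs the smaller p-value to fall below 0.05/2 = 0.025. If the tests are independent, the chance is 1 − 0.975² = 4.9%. The simulated value for one summary measure per tracer, with no baseline gap, is about 5%.

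**Cost in sensitivity.** For ANCOVA with one covariate on 17 degrees of freedom, solve 1 − F(t[1−α/2, 17]; 17, d√(10/2)) = 0.80 for d, where F is the noncentral t distribution function. This makes no allowance for chance baseline imbalance.
- α = 0.05: d = 1.33 residual SD.
- α = 0.025: d = 1.49 residual SD.
- Ratio: 1.49/1.33 = 1.12.

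For an assumed true difference of 1.0 residual SD, power is 56% at 0.05 and 43% at 0.025.

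**The case against.** The strongest reply is that Section 9.2 describes a small proof-of-concept study about feasibility, where strict error control is not expected. That lowers the stakes, but it does not settle the point. The Synopsis states a hypothesis test as the primary aim, and 9.4.1 declares significance. Section 9.2 also cites work that found no rise in false positives in small PET samples. As described there, that is a statement about sample size, not about testing many unranked outcomes.

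Three stronger readings are tempting, and the documents do not support them.

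- *Section 9 makes cognition the study's primary outcome.* The sentence sits inside the cognitive aim and is followed at once by the ranking of components below composites. The natural reading is local to Aim 1, and 1.1, 3 and 4.1 consistently put PET first. The wording needs cleaning up, but it does not show that the primary endpoint was switched.
- *The comparison itself is undefined.* Section 3's objective, "To assess whether 8-week administration of estrogen alters brain glucose and ketone body uptake in women with and without type 2 diabetes", could be taken as change within each group. However, 1.1 asks whether effects "differ in postmenopausal women with and without type 2 diabetes", the hypothesis in 2.2 and the design statement in 4.1 say the same, the Aim 2 heading concerns modification by diabetes, and the ANCOVA compares groups. The between-group question is clear.
- *The lack of blinding is what permits selection.* A blinded study with the same unranked list would have the same problem. Prespecification is the remedy.

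**Conclusion.** The point holds and should be fixed. The primary objective is clear, but the test that answers it is not named, and Section 9.4.1 allows a claim at 0.05 on any of 12 PET tests. If there is no true group difference and no baseline gap, the chance of at least one nominally significant PET result is well above 5% at every correlation tried: about 14-24% for the six regional uptake tests and about 19-41% for all 12, with 46% as the value under independence.

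The exact size depends on correlations that the documents do not give, and on one averaged value per region. That no PET test is ranked and no multiplicity rule exists rests on the text alone.

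This finding is about multiplicity only. Whether baseline-adjusted ANCOVA is biased when these non-randomized groups differ at baseline is a separate issue, and Holm does not address it.

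**What to change.** 1. In Section 9.1, put the PET aim first. Replace the sentence on composite scores with: *Within the secondary cognitive aim, the composites are the main outcomes; individual components are examined after them.*
2. In Section 9.1, add: *The two primary tests are the baseline-adjusted group differences in whole-brain FDG uptake and whole-brain AcAc uptake, with Holm control at 0.05 across the two.* Carry this into 1.1 and 3. Whole brain is already a listed measure. If the sponsor prefers a regional measure, name one and define its region identically in 1.1 and 9.1, with the precuneus either in or out in both.
3. In Section 9.4.1, limit confirmatory p<0.05 claims to those two tests. Report regional and ratio PET measures as exploratory estimates with 95% confidence intervals. The cognitive composites can keep their planned tests if they are labelled secondary.
4. Make the change in a dated amendment before any follow-up uptake data are analysed. If such data have already been analysed, say so and label the choice post hoc.

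The cost is an amendment with IRB approval, as the Statement of Compliance requires, with no new visits or data. The first Holm step at 0.025 raises the effect detectable with 80% power by about 12%, from 1.33 to 1.49 residual SD. Regional and ratio findings lose stand-alone confirmatory status.

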Three compounds are generally referred to by the term 'ketone body': acetone, acetoacetate (AcAc) and 3-betahydroxybutyrate (BHB). Acetone is considered to have limited significance in metabolism. The rate of ketone metabolism in the brain is regulated primarily by blood concentration, and secondly by blood brain barrier transport. Ketone bodies enter the brain via diffusion and monocarboxylic acid transporters (MCT1 and MCT2). Elevating circulating ketones, either through infusion or during diabetic ketoacidosis, results in parallel increases in brain metabolism of AcAc and BHB. Persistently high levels of ketones, which can occur through prolonged fasting (3.5 days) or a ketogenic diet, increase permeability of the blood-brain barrier to ketones, suggesting an upregulation of transporters. Current evidence suggests that circulating ketones are upregulated in people with T2D. This observation supports the idea that ketone bodies may be a viable supplemental bioenergetic substrate in people with T2D, because increased levels of circulating ketones augment availability of ketones to the brain. The premise of this study is to test the HCB theory of estrogen action in humans by measuring brain metabolism of ketone bodies and glucose using a novel dual-tracer PET method before and after administration of estradiol in women with and without diabetes.

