### Hypothesis

Estrogen affects brain metabolism of ketone bodies and glucose differently in women with T2D and those without, in accordance with the healthy cell bias theory of estrogen action.

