### Strengths and Weaknesses of Supporting Data

- 1) Previous results showing interaction between T2D and estrogen or gender on brain and cognitive outcomes are all large trials or epidemiological studies; characterization of T2D in these studies lacks relevant details. The WHIMS studies have the advantage that WHIMS is a randomized trial, so the observed effects of estrogen on cognitive and brain imaging outcomes are less likely to be attributable to biases or a confounding factor, as potential confounding factors should be approximately equivalent between the groups. Our study will be an important contribution by examining this potential effect with rigor and detail.
- 2) The dual-tracer PET has been successfully used to assess difference in ketone body and glucose uptake in healthy younger and older adults and older adults with cognitive impairment. Our preliminary data from an ongoing study (Fig. 2, section 3.4) show the method is sensitive to increased ketone uptake in response to a dietary intervention. Elevated ketone body levels have been observed in people with T2D, but the number of studies is currently small. There is not good representation of women and no research that we know of assessing circulating levels of ketone bodies in people of non-European descent with T2D.

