**PET scan procedure.**

- Subjects will report to the ground floor of the MRI building to the Molecular Imaging Research PET/CT scanner at Wake Forest Baptist Medical Center.
- Vital signs (blood pressure, heart rate, temperature) and body weight will be within 30 minutes of radiotracer injection.
- An indwelling catheter will be placed into a forearm vein in both arms.
- 30 minutes prior to the PET scan, a heating pad is wrapped around one arm (44 degrees Celcius). Up to 10mL of blood for Glucose, AcAc, and Beta-hydroxybutyrate (or BHB, the other major ketone body) quantification. This blood is stored on ice and immediately processed for analysis after the PET scan.

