**Alternate hypotheses.** In addition to its effects on cellular bioenergetics, estrogen can affect vascular health. A recent finding that women with T2D were at increased dementia risk saw increased risk for vascular dementia. Thus, the interaction between T2D and estrogen may be mediated through vascular effects, or through an interaction between metabolic and vascular effects. Therefore, we have included two MRI scans to assess vascular brain health: 1) a T2-weighted FLAIR image to assess white matter hyperintensities, an indicator of small-vessel disease correlated with diabetes status and hypertension, and 2) a susceptibility-weighted image to assess for microbleeds.

The 3 City Study found interactions between T2D status and endogenous estrogen levels. The WHIMS study observed an interaction between T2D and women randomized to oral estrogen treatment. We will examine exploratory cross-sectional associations between estrogen levels before estrogen administration and PET and cognitive testing to assess for differences due to endogenous estrogen.

Both the WHIMS and 3 City studies statistically adjusted for BMI. To minimize any potential influence of BMI that may persist after BMI adjustment, we plan to limit participants' BMI range and match for BMI. We will also examine whether changes in BMI or diabetes treatment over follow-up affect results. Cortisol may be elevated in older adults with T2D, even after controlling for BMI and the presence of cortisol may modify the effects of estrogen on cognition. Therefore, serum cortisol will be assayed to test for potential interactions between estrogen and cortisol. Due to the cyclical nature of cortisol secretion, all blood draws will occur between 8AM-10AM. OGTT data will allow us to use glucose and insulin levels as covariates as needed. [name] are currently collecting pilot data on methods that may enhance the sensitivity of the [C]AcAc scans. If these methods are successful, they will be incorporated into the final study.

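### Scan-day plasma glucose and ketones are collected but have no role in the Aim 2 inference, so a group difference in brain uptake, chiefly of ketones, cannot be attributed to brain handling rather than circulating substrate

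*Combined protocol and SAP*

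**What the plan says.** The hypothesis in section 2.2 is mechanistic: "Estrogen affects brain metabolism of ketone bodies and glucose differently in women with T2D and those without", in line with the healthy cell bias theory.

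The same section says "The rate of ketone metabolism in the brain is regulated primarily by blood concentration, and secondly by blood brain barrier transport". It adds that raising circulating ketones raises brain ketone metabolism in parallel, and "Current evidence suggests that circulating ketones are upregulated in people with T2D". Preliminary data are cited to show that "the method is sensitive to increased ketone uptake in response to a dietary intervention".

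Section 8.1 (PET scan procedure) provides for a draw about 30 minutes before the scan: "Up to 10mL of blood for Glucose, AcAc, and Beta-hydroxybutyrate". Scans take place at V2, before estradiol, and at V4, in week 8.

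Section 9.1, Aim 2, states "This will quantify absolute global and regional uptake of FDG and AcAc to determine uptake" and adds the ratio of AcAc to FDG uptake. "Inference will be based the same approaches as for cognitive data", which means ANCOVA on the follow-up value adjusted for baseline, with age, BMI and education examined as covariates. The one mention of a blood substrate in the analysis is "OGTT data will allow us to use glucose and insulin levels as covariates as needed".

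**The concern.** By the protocol's own account, the first determinant of brain ketone metabolism is how much ketone is in the blood. If plasma ketones change more in one group than in the other between V2 and V4, uptake can differ by group while the brain's handling of ketones stays the same. Any separate cause would do: estradiol acting outside the brain, diet or glycaemic drift. The ketone/glucose ratio inherits the problem through its numerator.

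There is no untreated arm, so a drift confined to one group cannot be subtracted. The rival explanations listed in section 9.1 are vascular effects, endogenous estrogen, BMI, diabetes treatment and cortisol. A change in circulating substrate is not among them, although the data to examine it will exist for every woman scanned twice.

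The OGTT covariate does not fill the gap. According to the Schedule of Activities (1.3), the OGTT is done once, at screening, and not in women with a diagnosis of diabetes or prediabetes. It cannot describe change from V2 to V4, it is missing in diagnosed women, and it is not described as measuring ketones.

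What is at stake is the mechanistic reading, which is the purpose of this proof-of-concept study.

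**Working it through.** **Reading the plan.** Section 9 was checked for any use of scan-day glucose, AcAc or BHB as outcome, covariate, mediator or sensitivity variable. There is none. Changes over time do enter elsewhere: 9.1 relates changes in PET outcomes to changes in cognition, and examines changes in BMI and diabetes treatment. Neither uses plasma substrate. The documents state no power, effect size or SD, so there is no figure to reproduce.

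**Inputs.** From the documents: 10 women per group and p<0.05 (taken as two-sided; the plan does not say). All else is assumed: absolute uptake U = rate constant k × plasma concentration C; SD of log change 0.15 to 0.25 for k (sK) and 0.30 to 0.50 for C (sC); no group effect on k; C rising D% more in one group.

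**Formulas.** Change in log U = change in log k + change in log C, so SD = √(sK² + sC²). The standardised difference is d = ln(1+D)/SD. The chance of p<0.05 comes from the noncentral t with 18 df and noncentrality d√(10/2).

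Example: sK = 0.20 and sC = 0.40 give SD = √(0.04 + 0.16) = 0.447. For D = 30%, d = 0.262/0.447 = 0.587, noncentrality = 0.587 × 2.236 = 1.31, and the chance is 0.237.

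| sK, sC | SD | D = 10% | D = 30% | D = 50% |
|---|---|---|---|---|
| 0.15, 0.30 | 0.335 | 0.092 | 0.381 | 0.725 |
| 0.20, 0.40 | 0.447 | 0.074 | 0.237 | 0.484 |
| 0.25, 0.50 | 0.559 | 0.065 | 0.169 | 0.336 |

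**Planned ANCOVA, simulated** (20,000 runs; sK = 0.2, sC = 0.4; baseline SDs 0.2 and 0.4; baseline plasma 30% higher in diabetes). The chance of p<0.05 for uptake is 4.8%, 7.5%, 22% and 43% at D = 0, 10, 30 and 50%. The same ANCOVA on k stays at about 5%.

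**Other assumptions** (6,000 runs; SD of change in log k 0.10, baseline SDs 0.15 for k and 0.40 for plasma). At D = 10, 20, 30 and 50%, the planned ANCOVA gives 15%, 38%, 67% and 96% if sC = 0.20, and 8%, 16%, 24% and 52% if sC = 0.40. ANCOVA on k again stays at about 5%. The pattern is stable, but the size depends on the inputs.

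**Precision.** The half-width of the 95% CI on the log scale is 2.101 × √(2/10) × SD = 0.940 × SD. For uptake this is 0.315 to 0.525, a factor of 1.37 to 1.69. For k it is 0.141 to 0.235, a factor of 1.15 to 1.26.

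**Which decision rule works.** In the model of the table (100,000 runs per setting, t-test on log change, D from 10% to 50%, no brain effect), k pointed the same way as a significant uptake difference in 58% to 83% of runs. It reached p<0.05 in that direction in about 3% to 12%.

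**The case against.** The strongest reply is that uptake is the stated endpoint (synopsis, section 3, Aim 2). If estradiol changes plasma ketones more in one group and uptake follows, uptake has truly changed and the ANCOVA is right to detect it. This stands. A reader might take the percentages above as an inflated false positive rate for Aim 2. They are not: they are the chance of detecting a real difference in uptake that arises outside the brain.

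A reader might also infer that a differential shift is expected. The documents do not say so. Higher ketones in diabetes is a difference in level, and baseline uptake is already in the model. No passage says that estradiol changes circulating ketones differently by diabetes status. Several design features also limit drift: a 6 to 7 hour fast before both scans, exclusion of metformin and insulin users, a restricted and matched BMI, and a planned look at changes in diabetes treatment. These narrow the routes but do not measure the substrate. A fixed fast sets fasting hours, not blood levels.

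The argument is weaker for glucose. The documents make no statement about plasma glucose and brain uptake comparable to the one about ketones.

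Finally, quantification follows a cited method that is not available here. Plasma values may enter that calculation, and the method may yield a rate constant. That could supply the measure proposed below, but the plan does not name it or give it a role in inference.

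**Conclusion.** The point holds as a gap in interpretation. The planned ANCOVA validly tests the total effect on uptake. It cannot separate changed brain handling from a different change in circulating substrate concentration, and the hypothesis is about the former. This matters most for ketone uptake and the ketone/glucose ratio, and less for FDG.

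The size is unknown. Across the two sets of assumptions, a plasma difference of 10% to 50% with no brain effect yields p<0.05 for uptake in about 7% to 96% of trials. That range reflects the absence of SDs and expected shifts in the documents and is not an estimate for this trial. It also rests on uptake being the product of a rate constant and plasma concentration.

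The change is worth making because the data are already collected, and with 20 women an explanation chosen after seeing the results would carry little weight.

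**What to change.** In section 9.1, Aim 2:

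1. Keep absolute uptake as the outcome, with the planned ANCOVA. Do not simply add V4 plasma level to that model, because estradiol may itself change it.
2. Tabulate pre-scan plasma glucose, AcAc and BHB at V2, at V4 and as change, by group, with 95% CIs.
3. Pre-specify a supportive ANCOVA, mainly for AcAc and secondarily for FDG, on uptake divided by same-scan plasma concentration, or on the rate constant if the cited method yields one. State which.
4. Claim a brain-level effect only if the 95% CI for the group difference on that measure excludes no difference. Agreement in direction is not enough, as the last step of the check shows. Otherwise report the uptake difference as not separable from changed substrate supply.
5. If a glucose covariate is used, take a fasting value available in both groups (V1 or V2) in place of OGTT data.

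Cost: one table and one extra result per tracer, with no new visit or sample. The supportive estimate will be imprecise with 10 per group. The separation is also imperfect, because section 2.2 notes that persistently high ketones can themselves increase transport into the brain.
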